1.1. Revision Date(s) add rows as needed			

[figure not shown]
TITLE: Cannabidiol (CBD) for the management of emergency dental pain

2. Background

Briefly discuss the important literature relevant to the trial and that provides background for the trial. Include the importance of the trial and any relevant treatment issues or controversies.

Dental pain can be devastating and often hard to treat effectively and safely. Endodontic pain is being routinely managed with root canal treatment often combined with pharmacologic agents, nonetheless post-operative pain often occurs, especially in cases with pre-operative pain (1, 2). Current analgesic regimens in endodontics mainly include non-steroidal anti-inflammatory drugs (NSAIDS) and acetaminophen often combined with opioids (3-5). These drugs, besides their large variability in effectiveness, are also associated with moderate to severe side-effects that range from gastrointestinal bleeding disorders to liver/kidney damage, cardiovascular effects and even death (6-8). CBD, which is the primary non-psychoactive and non-addictive compound in cannabis, is currently FDA-approved for the treatment of epileptic seizures, and has already shown potential in treating pain such as arthritis, neuropathic, cancer and chronic pain (9-12). The rational leading to this project is that the use of CBD, a cannabinoid with no psychoactive and addictive effects and mild-to-moderate side effects, may provide a better alternative to these analgesics for dental pain (13, 14). Further, we propose to study in our clinical model the already FDA-approved CBD formulation (Epidiolex, GW Pharmaceuticals) *off-label*, thus ensuring that the drug, if successful, could be more readily available for our dental patients. Notably, the alternative CBD formulation will aim to reduce the rate of opioid prescriptions for dental pain and provide a significant relief to the opioid epidemic. Reported CBD-related AEs after long term use include gastrointestinal effects, sleep disorders and elevated liver transaminases (15, 16). Events after short-term use, which is typically the schedule for dental pain, are not reported (14, 16). Collectively, it is important to note that we do not propose to replace opioids with another drug that can develop psychotic disorders and addiction, nor does our proposed used of CBD present with significant known AEs as often seen with NSAIDS and acetaminophen.

Preliminary data. We isolated TG neurons from C57BL/6 female mice and cultured them for 5 days. This assay takes advantage of a reporter dye (Fura-2) that increases fluorescence by an influx of calcium into the cell, thus providing a measure of neuronal activation. Briefly, TG neurons were incubated with Fura-2AM, then pretreated with CBD (1-1000uM) or vehicle for 5 min. A major subclass of nociceptive ("pain detecting") neurons were then stimulated with capsaicin (15nM for 40s) and

intracellular calcium levels $[Ca^{+2}]_i$ were recorded using a FlexStation 3 (Molecular Devices). The net changes in $[Ca^{+2}]_i$ were calculated by subtracting the baseline $[Ca^{+2}]_i$ (mean value collected for 60s prior to addition of CBD) from the Max $[Ca^{+2}]_i$ value achieved after exposure to the drugs. Preliminary data show that CBD 100uM and 1000uM significantly inhibited capsaicin-induced $[Ca^{+2}]_i$ accumulation. These preliminary data support our central hypothesis that CBD produces analgesia via peripheral inhibition of TG nociceptive neurons.

3. Objectives and Endpoints All data points collected in the study should support an objective or have a regulatory purpose. Complete the table – add rows as needed.		
3.1. Objective(s) Clearly and concisely define the primary and secondary outcomes.	3.2. Endpoint Clearly define the endpoints. (endpoints are the basis for concluding that the objective has been met).	3.3. Justification for Endpoint Briefly explain why the endpoint(s) were chosen.

1. Primary outcome measure: a.VAS pain intensity differences from baseline among the groups at each time point and maximum pain relief.
 
b.Bite Force measurement using the Bite Fork at baseline, 1.5 h, 3h and 7d.
 
2. Secondary outcome measure: Measure psychoactive effects, mood changes at 0, 1.5h and 3h points, and somnolence at 3h and 1- week time point.
	
1. Patients will report their pain level using a 100mm Visual Analogue Scale (VAS) at 0, 15min, 30min, 45min, 1h, 1.5h, 2 and 3 hour and 1week post-administration visit time of study drug Epidiolex or Placebo.
 
2. Patients will report their pain level that is elicited by biting down on the Bite Fork at 0, 1.5h, 3h and 1week post-administration visit time of study drug Epidiolex or Placebo.
 
2. Patients will report feelings of drug high, alterations in internal perception and alterations in external perception, along with alertness, contentment and calmness by completing the following questionnaires:
 
a. Bowdle questionnaire b. Bond & Lader Mood Scale c. Epworth Sleepiness Scale
	
1. The VAS has been shown to be sensitive to changes in a patient's pain experience, is easily understood and easy to use. It has been successfully used in various health fields in children and adults.
 
2. The bite force measurement provided additional pain information being able to isolate one particular tooth (the problem tooth) being studies.
 
2. The three listed questionnaires are commonly used for psychedelic assessment and safety assessment of cannabinoids use, with a longstanding administration in previous published studies in medical journals such as "Pain", "CNS Drugs", and "Journal of Psychopharmacology". Such effects are not commonly associated with CBD use because of the inherent nature of the absence of THC based on current literature. Nevertheless, patients that report such adverse events at the end of the observation period will be asked to have a family member to accompany them home.

4. Rationale Briefly state the reason for conducting the clinical trial.			

CBD is currently being tested in ~155 clinical trials for various disorders, with 16 of those trials assessing pain outcomes including one new study assessing analgesic efficacy of CBD after tooth extractions (www.clinicaltrials.gov, accessed March 2020). By an unusual regulatory circumstance, synthetic CBD is a Schedule I drug, whereas hemp-derived CBD is a Schedule V drug. Accordingly, we propose to use the FDA-approved cannabis-derived CBD (Epidiolex, Greenwich Biosciences, CA). Epidiolex is the first, and thus far only, FDA-approved Schedule V CBD oral solution designated for rare forms of epileptic seizures. The objective here is to test Epidiolex off-label for the treatment of emergency tooth pain in a human clinical trial. We hypothesize that Epidiolex will provide substantial pain relief for the patients presenting with emergency odontalgia in our clinical research facility.
			

5. Study Design			
5.1. Number of Groups/Arms	3	Group name(s)	1. CBD 10mg/kg single dose (given one time only) Epidiolex 100mg/ml oral solution 2. CBD 20mg/kg single dose (given one time only) Epidiolex 100mg/ml oral solution 3. Placebo oral solution single dose (given one time only)

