2. Self-reported prior experience inhaling cannabis (either via smoking or vaporization). Cannabis trials often present with high placebo effect. Cannabis naïve subjects are thus proposed to minimize this effect as well the possibility of tachyphylaxis.

3. Use of opioids in the month prior to screening/treatment visit, and/or NSAIDS or acetaminophen 6 hours prior to treatment. Any analgesic can potentially mask the effects of the study drug and increase placebo effect.

Continued Study Monitoring and Halting Rules:

Study drug is administered one time only at study hour zero with monitoring for the next three hours. Once the assigned study drug is given, the subject will continue in the 3-hour study observation period, even if they request the rescue medication. Only if they specifically request to formally withdraw from the study will they proceed to the dental treatment early, however subjects will be asked to complete the 3rd hour pain and Psychoactive Assessment Questionnaires at the time of consuming the rescue medication. Each patient is different in regards to their pain endurance level, so subjects will be instructed to request rescue medication when their pain becomes uncomfortable. Subjects will be encouraged to wait at least 60 minutes after the one time administration of the study drug before consuming any rescue medication. Subjects will additionally be asked to attend the one-week follow-up visit and complete the VAS and Sleepiness Scale Assessment.

In the case that a serious event appears within the same arm more than three times, we will discontinue the arm of the study. The PI will unblind the cases for close monitoring of the adverse event.

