12.2. Sample Size Determination

Include number of participants to recruit, screen, and enroll to have adequate power to test the key hypotheses for the study. Provide all information needed to validate your calculations and judge the feasibility of enrolling and following the necessary number of participants.

This is a pilot clinical trial to determine the necessary effect size for an appropriately powered definitive clinical trial that will be pursued in a subsequent R01 (or UG3/UH3) application submitted to the NIH. We plan to enroll a convenience sample of N=22/group. We note that prior definitive studies in this pain model have detected NSAIDs such as ibuprofen with a similar sample size (17, 18).

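### Somnolence 3 h after a single dose appears to rest on the Epworth scale, which is not designed to register acute sedation; the alertness score already collected fits the question better

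*Combined protocol and SAP*

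**What the plan says.** The secondary outcome in section 3.1 has two parts on different schedules. The first is "Measure psychoactive effects, mood changes at 0, 1.5h and 3h points". The second is "somnolence at 3h and 1- week time point". No time-0 reading is listed for somnolence.

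Section 3.2 says what patients report: drug high, altered internal and external perception, "along with alertness, contentment and calmness by completing the following questionnaires". Three forms follow: the Bowdle questionnaire, the Bond & Lader Mood Scale, and "c. Epworth Sleepiness Scale". The text does not match forms to constructs or to times. Section 7 refers the timing to the schedule of events, which section 8.7 treats as an attachment, and it is not part of the text reviewed here.

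Section 3.3 justifies all three forms together, as "commonly used for psychedelic assessment and safety assessment of cannabinoids use". It gives no recall period, no adapted wording for present sleepiness, and no reason why the sleepiness form suits a 3 h window.

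On exposure, section 11.1 states: "Study drug is administered one time only at study hour zero with monitoring for the next three hours". The same section asks patients to return at one week and "complete the VAS and Sleepiness Scale Assessment". Section 12.4 plans mixed models for the secondary outcomes and chi-squared tests for adverse events.

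**The concern.** With one dose at hour zero, a somnolence reading at 3 h can only be meant to show whether that dose made the patient sleepy. A form that asks how likely someone usually is to doze in daily life addresses a different period, most of which lies before the dose. A patient who is drowsy now may answer much as they would have answered that morning. A time-0 Epworth would supply a baseline, but both readings would still cover nearly the same stretch of ordinary life. The one-week reading does not help with the acute question, because it comes seven days after a single dose with dental treatment in between.

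What is at stake is how a null result is interpreted. The Background (section 2) says that events after short-term use have not been reported, so this trial would supply some of the first acute data in this setting. An insensitive score could turn that gap into apparent reassurance. Section 12.4 also says the analysis will inform the choice of endpoints for the main study, so a poorly matched endpoint could be carried forward.

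**Working it through.** The plan states no effect size, SD or power for somnolence, so there is no figure to reproduce. Section 12.2 says only "We plan to enroll a convenience sample of N=22/group", which is 3 × 22 = 66 patients.

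**Step 1: match construct, form and time.**

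| Construct | Likely form | Times in 3.1 | Time-0 value | Period asked about |
|---|---|---|---|---|
| Somnolence | Epworth (only sleepiness scale listed) | 3 h, 1 week | none listed | usual daily life (assumed standard wording) |
| Alertness | Bond & Lader (natural reading of the list) | 0, 1.5 h, 3 h with the mood measures | yes | current state (assumed) |

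The link from the Epworth to somnolence is an inference. It is supported by section 11.1, which places a sleepiness scale at one week, and by section 7, which has sleep questionnaires after dosing and again at one week. That pattern fits the somnolence schedule. The link from Bond & Lader to alertness is likewise read from the list.

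**Step 2: illustrate what partial sensitivity costs.** Inputs from the plan are 22 per arm and α = 0.05. Assumptions are a two-sided test, the normal approximation, one pairwise comparison, no dropout and SD = 1. Let f be the fraction of the true standardized effect that the 3 h score passes on. The documents say nothing about f, so the whole range is shown.

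- Standard error of the difference: √(2/22) = 0.3015.
- Effect with 80% power: (1.960 + 0.842) × 0.3015 = 0.84 SD (0.86 by t-test).
- Power at fraction f: Φ(f × δ / 0.3015 − 1.960).
- Example, δ = 0.845 and f = 0.5: Φ(1.401 − 1.960) = Φ(−0.559) = 29%.

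| True effect δ | f = 1 | 0.75 | 0.5 | 0.25 | 0 |
|---|---|---|---|---|---|
| 0.84 SD | 80% | 56% | 29% | 10% | 2.5% |
| 0.5 SD | 38% | 24% | 13% | 6% | 2.5% |

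At f = 0, the 2.5% is chance significance in that direction.

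**Step 3: what a time-0 value adds.** Adjusting for a baseline with correlation r to the follow-up score multiplies the residual SD by √(1 − r²). At δ = 0.84 SD, fully registered:

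- r = 0.3: factor 0.954, power 84%.
- r = 0.5: factor 0.866, power 90%.
- r = 0.7: factor 0.714, power 98%.

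Alertness is itself a proxy, so full registration may be generous. If alertness passes on three quarters of the effect and r = 0.5, then 0.75 × 2.802 / 0.866 = 2.427, and Φ(2.427 − 1.960) = 68%. The 80% case without baseline becomes 68% here, compared with 29% for an unadjusted score that passes on half. All values of f and r are assumptions. The table shows how the loss behaves and does not estimate it for this trial.

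**The case against.** The strongest objection is that the protocol nowhere describes what the Epworth asks. The point depends on the standard wording of a named scale, and an adapted form could be in use. This stands as a condition on the conclusion. The protocol names the scale without qualification and mentions no adaptation, so the standard form is the reasonable assumption. Stating the recall period would settle the matter.

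A reader might infer that the Epworth cannot register acute sedation at all, so that the 3 h contrast must be about zero. The documents do not support this. Present drowsiness can colour answers about usual dozing, and nothing in the plan fixes f at zero.

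A reader might also infer that sedation would go undetected, or that the protocol itself lists it as an effect of the drug. Neither holds. Alertness is reported, adverse events are compared between arms (section 12.4), and clinical staff observe patients throughout the 3 hours (section 10.2). Section 3.3 also has patients who report psychoactive effects at the end of observation accompanied home. The Background ties sleep disorders to long-term use, and a sleep disorder is not the same as sedation after one dose.

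Two further objections stand in part. Alertness is not identical to somnolence. Codeine-containing rescue, allowed during observation by sections 10.3 and 10.4, can lower alertness for reasons unrelated to the study drug. Both limit how the proposed endpoint should be read, but neither makes the Epworth the better measure at 3 h.

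**Conclusion.** The concern holds as a mismatch between instrument and time frame. The only sleepiness scale listed is, on its standard wording, not designed to register sedation in the hours after a dose, and no time-0 reading is listed for it. Its sensitivity at 3 h is likely to be low, but the size of the loss cannot be derived from the documents. On assumed inputs, power falls from 80% to 29% if half the effect registers and to 10% if a quarter does.

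The practical consequence is that a null Epworth comparison at 3 h should not be reported as absence of acute somnolence. Under the current plan, sedation could still show in alertness or adverse events, but nothing says which result supports the somnolence conclusion. The matter is a secondary outcome in a pilot and no efficacy conclusion depends on it. It is worth correcting because the change is nearly free and the pilot is meant to guide later endpoints.

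The conclusion rests on three readings: standard Epworth wording, the Epworth as the somnolence measure, and Bond & Lader as the source of alertness at 0, 1.5 h and 3 h.

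**What to change.** - In sections 3.1 and 3.2, define acute somnolence as the alertness score at 1.5 h and 3 h, adjusted for its time-0 value, and analyse it in the mixed model already planned in section 12.4. State that the score comes from the Bond & Lader scale.
- Keep the Epworth only as a description of usual sleepiness, with its recall period stated. It should not be used as evidence on drug-induced somnolence at 3 h.
- State beside each form in section 3.2 its construct and its times, consistent with the schedule of activities.
- Report the alertness result with rescue use shown by arm, and describe alertness as a proxy for somnolence. The sections differ on the alternative to ibuprofen: section 7 names plain acetaminophen, while sections 8.1, 10.3 and 10.4 name the codeine combination. These need to be reconciled so that a reader can tell which rescue could affect alertness.

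The cost is endpoint wording and one analysis of data that, on the natural reading, are already being collected. There is no new form or visit, and the 3 h Epworth could be omitted.

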5.2. Overall Design Select all applicable			

	Randomization				Cluster Randomized								
	Group-Sequential				Adaptive Design								
	Parallel Design				Placebo-Controlled								
	Superiority				Equivalence				Non-inferiority				
Device			Pilot			Pivotal				Post-Approval			
Drug/Biologic			Phase 1		Phase 1/2		Phase 2		Phase 2/3		Phase 3		Phase 4
 Dose escalation		If yes, details →											
 Dose ranging		If yes, details →		10mg/kg single dose (given one time only) Epidiolex 100mg/ml oral solution vs. 20mg/kg single dose (given one time only) Epidiolex 100mg/ml oral solution									
 Sub-studies		If yes, details →											
5.3. Other Design Details: Double-arm phase II randomized placebo-controlled trial with quadruple masking (Participant, Care Provider, Investigator, Outcomes Assessor)													

6. Study Population

6.1. Study Population(s) Label/Name To add more populations – select a row, copy & paste	6.2. Identify the criteria for inclusion The criteria that every potential participant must satisfy, to qualify for study entry. All individuals in this study population must meet all of the inclusion criteria in order to be eligible to participate in the study	6.3. Identify the criteria for exclusion The characteristics that make an individual ineligible for study participation. All individuals in this study population meeting any of the exclusion criteria at baseline will be excluded from study participation.
Adults 18-75 years old with moderate-severe odontogenic pain	
 -Healthy adults 18-75 years old, ASA I or II. -Permanent tooth with moderate to severe odontogenic pain, i.e. ≥30 on a 100mm VAS, as reported verbally by the patient. -Clinical pulpal diagnosis of irreversible pulpitis or pulpal necrosis, and periapical diagnosis of symptomatic apical periodontitis. -Test negative for recent cannabis use and/or other drugs of abuse including alcohol (urine tests collected at screening visit. Results will be available on site within 3-5 minutes). -Participant able to understand the forms (English or Spanish) and provide informed written consent 	
 -ASA Class III or IV, patients with hepatic impairment, pregnant or lactating women (pregnancy test is performed at the screening visit). -Patients on drugs metabolized by enzymes that also metabolize CBD (e.g. clobazam, diazepam, topiramate, warfarin), or other drugs known to interact with Epidiolex (as assessed by PI at time of screening). -Self-reported prior experience inhaling cannabis (either via smoking or vaporization). -Use of opioids in the month prior to screening/treatment visit, and/or NSAIDS or acetaminophen 6 hours prior to treatment. -Unwilling to participate
6.4. Will screen failures be allowed to re-screen at a later date?	 No  Yes If yes, describe criteria below ↓	Since the patients present with emergency pain and their pain will need to be addressed in a timely manner with appropriate treatment, there won't be any re-screening.

7. Study Intervention(s) being tested or evaluated

This can include prevention, diagnostic or therapeutic interventions (e.g., drug or device) or educational, health services or basic science interventions (e.g., educational program, health care delivery model, or examining basic physiology)

This is a therapeutic intervention study where the FDA approved study drug used off-label in two different doses according to randomization will be assessed against a Placebo of similar taste and appearance.

Group 1: CBD 10mg/kg single dose (given one time only) Epidiolex 100mg/ml oral solution

Group 2: CBD 20mg/kg single dose (given one time only) Epidiolex 100mg/ml oral solution

Group 3: Placebo oral solution single dose (given one time only)

The objective here is to test Epidiolex off-label for the treatment of emergency tooth pain in a human clinical trial. We hypothesize that Epidiolex will provide substantial pain relief for the patients presenting with emergency odontalgia in our clinical research facility.

Patients who present to the UT dental clinics will be provided a standard of care dental exam assessing the oral problem that brought them to the clinic. A non-research, routine oral exam will be provided. If the patient has expressed pain as part of their dental problem, they will be approached by study staff to explain the study and inquire if the patient would be interested in entering the study. If interested, informed consent will be obtained and documented. Medical history, demographics, vitals, pain questionnaire, Bite Force measurement, and study oral exam will be completed. Height & weight of the patient will be obtained for calculation of study medication to be given. Screening labs (urine pregnancy test for women of child-bearing age and urine toxicology) will be completed for research purposes to confirm inclusion/exclusion criteria. Subjects who meet all eligibility criteria will proceed to randomization. Eligible subjects will be randomized in a 1:1 ratio to one of the three study intervention arms: Epidiolex 10mg/kg, Epidiolex 20mg/kg or Placebo. Rescue pain medication of Ibuprofen 600mg or Acetaminophen 500mg will be administered if needed. Pain, Psychoactive and sleep questionnaires will be completed following study intervention administration at the timepoints outlined in the schedule of events. A follow-up research visit will occur one-week post-drug administration where a research sleep questionnaire will be completed and oral exam data collected (pain assessment, reported issues post-treatment, any rescue medication used).

The following coding system will be used to ensure that participant identities remain confidential and to protect against disclosure. Each participant will be assigned a unique Study ID# and all study data collected will be coded with this number. The Study ID# will be linked to participants' names on the Participant Log which will be kept in a secure location separate from the coded study data and will be accessible only to members of the research team. Data collected for this study will be coded with a Study ID# and securely stored in the offices of the research team. Certain personal identifiers required to conduct the study but not for statistical analysis (name and phone numbers) will be kept separate from research data collected and not entered into REDCap. Certain personal identifiers such as date of birth and gender that are needed for statistical analyses will be entered into REDCap. REDCap is password-protected and HIPAA-compliant. Data entered into REDCap is stored on a secure UT Health server. All electronic data will be protected using password-protected computers. Government or university staff may review this study to make sure it is being conducted safely and legally.

The PI will be informed by study staff of any subject who experience an adverse event, whether during the study visits or during the one-week post-procedure time. The PI will proceed with unblinding of the subject's group. Depending on the nature and severity of the adverse event, the patient will be instructed to contact their physician or visit the urgent care clinic.

8. Protocol-Directed procedures, items, services or tests

List all procedures directed by the study plan - including items or services provided as part of routine or conventional care and those needed to diagnosis or treat research related complications.

Important Note – The protocol directed procedures listed must match those in the [Schedule of Activities \(attachment\)](#)

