10.1. Measures to Minimize Bias: Randomization and Blinding

This section should contain a description of randomization and blinding procedures (if applicable to the study design). It should include a description or a table that describes how study participants will be assigned to study groups, without being so specific that blinding or randomization might be compromised. Plans for the maintenance of trial randomization codes and appropriate blinding for the study should be discussed. The timing and procedures for planned and unplanned breaking of randomization codes should be included. Include a statement regarding when unblinding may occur and who may unblind. Provide the criteria for breaking the study blind or participant code. Discuss the circumstances in which the blind would be broken for an individual or for all participants (e.g., for serious adverse events (SAEs)). Indicate to whom the intentional and unintentional breaking of the blind should be reported.

REDCap will be utilized to create the randomization for treatment arm for all participants. Limited data will be entered into the REDCap software which will create a unique Study ID# for each participant. Randomization will also occur in REDCap per individual unique Study ID# created by the software.

Unblinding of a subject who has experienced an adverse event will be conducted by the PI by review of the online system of that particular subject's study e-chart and will occur within 24 hours of the AE notification. The PI will document and assess the unblinded information and appropriately report the AE, additionally make the appropriate treatment recommendations for the patient to ensure safety. In the case of serial adverse events of a similar type, or with a serious adverse event, the PI will unblind all participants and report to the IRB as required.

We will collect subject names and phone numbers to be recorded in the Participant Log in order to track when patients are scheduled for their regular clinic visits as research data collection will be linked to these regularly scheduled visits.

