12.3. Populations for Analyses

Clearly identify and describe the analysis datasets (e.g., which participants will be included in each).

All participants in all three groups will be included in the analyses. The 3 groups will be compared to each other. While we expect that randomization will lead to balanced groups, we will specifically assess for age and sex balance and perform sensitivity analyses, if indicated. Further, we will employ generalized estimating equation models accounting for correlation between pain measures at various timepoints to assess the timepoint when maximum analgesia is observed.

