12.4. Statistical Analyses

Include analysis of primary efficacy endpoints, secondary endpoints, safety analyses, and any planned interim analyses

This analysis will provide critical information for subsequent sample size calculations and endpoint determination in the subsequent main study. Mixed model analyses will be used for both primary and secondary outcomes. AEs among the groups will be analyzed with χ^2 tests. The time-to-rescue medication will be summarized using Kaplan-Meier curves and compared between groups using stratified log-rank tests. Level of significance will be set at $\alpha=0.05$. JMP software and GraphPad will be used for the analyses and the graphs.

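### The pain model names no baseline covariates: prespecify baseline VAS and pulpal diagnosis as fixed terms, for precision and chance imbalance rather than to correct bias

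*Combined protocol and SAP*

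**What the plan says.** - **Outcome.** Section 3.1 defines the primary pain outcome as the difference in VAS from baseline at each time point, plus maximum relief. Section 3.2 lists a baseline reading and eight later ones, from 15 minutes to one week.
- **Population.** Section 6.2 requires "Clinical pulpal diagnosis of irreversible pulpitis or pulpal necrosis", together with symptomatic apical periodontitis. Either pulpal diagnosis qualifies; the periapical diagnosis is common to all.
- **Size and purpose.** Section 12.2: "We plan to enroll a convenience sample of N=22/group". It also says: "This is a pilot clinical trial to determine the necessary effect size for an appropriately powered definitive clinical trial".
- **Allocation.** Section 7: "Eligible subjects will be randomized in a 1:1 ratio to one of the three study intervention arms". Section 10.1 says "REDCap will be utilized to create the randomization for treatment arm for all participants" and describes no strata.
- **Balance.** Section 12.3 keeps all participants together and says "we will specifically assess for age and sex balance and perform sensitivity analyses, if indicated". It gives no criterion for when such analyses are indicated. It also mentions generalized estimating equations to locate the time of maximum analgesia, again without covariates.
- **Model.** Section 12.4: "Mixed model analyses will be used for both primary and secondary outcomes". No fixed effects are listed. The log-rank test for time to rescue is described as stratified, but its strata are not named.

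**The concern.** Two baseline values that the trial must obtain for every patient have no stated role in the analysis. Baseline VAS is needed for eligibility and for the change score. Pulpal diagnosis is needed for eligibility. Subtracting baseline is not the same as adjusting for it: the change score forces a slope of 1 on baseline, and any other slope leaves removable variance in the outcome. Pulpal diagnosis divides the sample into two tooth conditions and could differ between arms of 22 by chance.

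The trial's product is an effect estimate, and a variance, for planning a definitive trial. Avoidable noise in either carries into that trial's sample size. Deciding on sensitivity analyses after looking at the observed balance also leaves a choice that could be closed now at no cost.

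**Working it through.** **Inputs from the documents.** There are three arms with 22 per arm, so 3 × 22 = 66 patients. The outcome is VAS change, and no stratification is described. The plan gives no effect size, SD, power or diagnosis mix, so it has no figure of its own to reproduce here.

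**Assumptions.** Simple randomisation; necrosis share p of 20%, 30% or 50%; difference δ in mean VAS change between diagnoses of 5-20 mm; residual SD of 25 mm; baseline-outcome correlation ρ of 0.3-0.7.

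**1. Chance imbalance in diagnosis.** The number with necrosis in each arm is Binomial(22, p), independent across arms. A gap of 5 of 22 is 5/22 = 23 percentage points. The exact probabilities of a gap at least that large are:

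| Necrosis share | One given pair | At least one of the two CBD-placebo pairs |
|---|---|---|
| 20% | 8.8% | 16% |
| 30% | 13.7% | 24% |
| 50% | 17.4% | 29% |

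The last column is 1 − Σ f(x)·g(x)², where f(x) is the probability that placebo has x cases and g(x) is the probability that one CBD arm lies within 4 of x. Counting the 10 versus 20 mg/kg pair as well raises it to 20%, 30% and 36%, but that pair is not a comparison of CBD with placebo.

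**2. Size of the resulting shift.** A 5-of-22 gap moves the unadjusted contrast by δ × 5/22:
- δ = 5 mm: 1.1 mm
- δ = 10 mm: 2.3 mm
- δ = 20 mm: 4.5 mm

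For scale, the standard error of a pairwise contrast is 25 × √(2/22) = 7.5 mm with diagnosis removed. Without adjustment, at p = 50% and δ = 20 mm, it is √((625 + 100) × 2/22) = 8.1 mm.

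**3. Variance removed by a diagnosis term.** The share is δ²p(1−p) / (625 + δ²p(1−p)).
- δ = 5, p = 20%: 4/629 = 0.6%
- δ = 5, p = 50%: 6.25/631.25 = 1.0%
- δ = 20, p = 20%: 64/689 = 9.3%
- δ = 20, p = 50%: 100/725 = 13.8%

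The range is therefore about 1-14%, and it is zero if diagnosis is not prognostic.

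**4. Variance removed by a baseline VAS term.** With equal variances σ² at baseline and follow-up, the change score has variance 2σ²(1−ρ) and the baseline-adjusted outcome has σ²(1−ρ²). The ratio is (1+ρ)/2.
- ρ = 0.3: 0.65, a cut of 35%
- ρ = 0.5: 0.75, a cut of 25%
- ρ = 0.7: 0.85, a cut of 15%

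The equal-variance assumption matters because entry requires a VAS of at least 30, which may narrow the baseline spread. In general the cut is (s−ρ)² / (s² + 1 − 2ρs), where s is baseline SD divided by follow-up SD. With s = 0.7 and ρ = 0.3 it is 0.16/1.07 = 15%. With s = ρ it is zero, because the slope on baseline is then exactly 1. Apart from the degrees of freedom spent, adjustment does no worse than the change score.

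**The case against.** **A reader might infer that pooling the diagnoses, or leaving them unadjusted, biases the CBD estimate.** It does not. Randomisation keeps the unadjusted contrast unbiased, and its standard error already includes chance imbalance. Even the 4.5 mm shift, from the largest assumed difference, is below one standard error.

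**A reader might infer that diagnosis must be adjusted for because it predicts pain.** The documents do not say that the two diagnoses differ in pain course or drug response, and all patients share the same periapical diagnosis. The mix, the difference in millimetres and the SD are all assumptions. This objection stands, and it is why the diagnosis term is the smaller part of the recommendation.

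**A reader might infer that the primary model is adjusted only when imbalance is seen.** Section 12.3 attaches that condition to sensitivity analyses, not to the primary model.

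**The cost may exceed one degree of freedom.** This also stands. A single diagnosis term removes the imbalance at every time only if its effect is constant. Letting it vary over eight post-dose times takes up to 8 degrees of freedom, and baseline VAS the same.

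**Diagnosis may not be an available variable.** It has to be established for eligibility, but sections 7 and 8 do not list it as a data item, and the Schedule of Activities is a separate attachment that is not part of the text reviewed.

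**For a pilot with a convenience sample, this may look like preference among covariates.** In part it is. However, the pilot exists to supply an effect size and inform later sample-size calculations, so precision is relevant to its stated purpose.

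**Conclusion.** The point holds as a small, inexpensive improvement in precision and a safeguard against chance imbalance. The plan's validity is not in question. The main element is baseline VAS: a 15-35% cut in variance relative to an unadjusted change score under equal variances and a correlation of 0.7-0.3, and less if the entry threshold compresses baseline. Pulpal diagnosis is secondary: about 1-14% under the stated assumptions, and nothing if it is not prognostic. A 5-of-22 imbalance affecting at least one CBD-placebo comparison is far from rare (16-29% over the assumed mixes), so reporting diagnosis by arm is worthwhile whatever its prognostic strength.

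**What to change.** - **Section 12.4:** set the fixed effects of the pain model in advance as arm, time, arm-by-time, baseline VAS and pulpal diagnosis. Give each of the last two a time interaction if its effect may vary over time. If the baseline VAS is kept as a response in the model instead, constrain the arms to a common baseline mean, which plays the same role as the covariate.
- **Data collection:** record pulpal diagnosis as a data item and report it by arm.
- **Section 12.3:** replace the conditional sensitivity analyses with one fixed age- and sex-adjusted sensitivity model.
- **Randomisation:** leave unchanged.

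**Cost.** A few sentences, one recorded field drawn from the eligibility examination, and a few degrees of freedom in about 66 patients (more if both time interactions are used). If diagnosis proves uninformative, its term yields little. The work is best done before any unblinded data are seen.
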